10.2 Recording Adverse Events (AEs)

A record of all AEs, whether related or unrelated to study participation will be kept in the CRF and the Sponsor's AE Log JRESLOG0007. We will not record AEs which can reasonably be considered to be part of pregnancy including nausea, vomiting, back, hip or pelvic pain, abdominal discomfort, reduced sleep, constipation and lower limb swelling.

If the investigator suspects that the disease or condition has progressed faster due to the intervention, then they will report this as an unexpected adverse event to the sponsor.

10.3 Investigator Responsibilities relating to Safety Reporting

Collection, recording and reporting of AEs (including serious and non-serious events and reactions) to the Sponsor will be done according to the Sponsor's Safety reporting for non-CTIMP studies SOP JRESSOP0033.

All SAEs will be recorded in the CRF, and the Sponsor's AE Recording Log JRESLOG0007. The AE Log will be sent to the Sponsor on request and every 2 months.

All SAEs will be reported both to the Sponsor via the JRES & REC using the SAE report form for research other than CTIMPs (non-CTIMPs) published on the HRA website. The Chief or Principal Investigator at any participating site will complete the SAE form which will be faxed to the JRES on [name] or e-mailed to [contact], within 48hrs of the Investigator becoming aware of the event, and via email to the relevant REC.

The Chief or Principal Investigator will respond to any SAE queries raised by the Sponsor as soon as possible. Follow up reports must continually be completed within acceptable time-frames and sent as detailed above until the reportable event is considered resolved

Events will be followed up until resolution; any appropriate follow-up information will be clearly marked as such and reported to the sponsor via the JRES as above in a timely manner.

Full reports should be completed and submitted to REC within 15 days of the event

10.4 Notification of deaths

All deaths will be reported to the Sponsor irrespective of whether the death is related to disease progression, the intervention, or an unrelated event.

11 Data management and quality assurance

11.1 Confidentiality

St George's, University of London is the sponsor for this study and is based in the United Kingdom. They will be using information from participants (directly and/or medical records) in order to undertake this study and will act as the data controller for this study. All data will be handled in accordance with the Data Protection Act 2018.

The Case Report Forms (CRFs) will not bear the participant's name or other directly identifiable data. The participant's trial Identification Number (ID) only, will be used for identification. The sponsor Subject ID log JRESLOG0002 can be used to cross reference participant's identifiable information.

11.2 Data collection tool

Case Report Forms will be designed by the CI or a delegated member of the study team. All data will be entered legibly in black ink with a ball-point pen. If the Investigator makes an error, it will be crossed through with a single line in such a way to ensure that the original entry can still be read. The correct entry will then be clearly inserted. The amendment will be initialled and dated by the person making the correction immediately. Overwriting or use of correction fluid will not be permitted.

It is the Investigator's responsibility to ensure the accuracy of all data entered and recorded in the CRFs. The Staff Delegation of Responsibilities Log JRESLOG0004 will identify all trial personnel responsible for data collection, entry, handling and managing the database.

Data will be recorded directly onto the CRF.

An initial entry will be made in the participant's handheld notes describing the participant's involvement in a research study. The front page of the handheld notes will have a sticker placed on it to alert clinical staff to study participation. Any further correspondence between the study team and clinical colleagues will take place by letter.

There are three types of study-specific questionnaires to be completed throughout the study period (background and contact questionnaires at Visit 1, contact questionnaire at Visit 2 and 3, contact and feedback questionnaires at Visit 4). At Visit 1 and 4 which require face to face contact, the questionnaires will be completed electronically on an electronic device (and if not possible on hard copy). For Visit 2 and 3, a link to the contact questionnaire will be emailed out to participants along with a text. If participating women do not have access to a computer, the questionnaire may be mailed to them and a pre-paid envelope provided.

11.3 Incidental Findings

In this study the participants' newborns are offered screening for evidence of cCMV. A positive CMV salivary swab result will be communicated to the participants by phone by a clinically qualified member of the research team and arrangements will be made for appropriate clinical follow up. This will involve referral to the paediatric infectious diseases team, according to established clinical pathways. Whilst a discovery of cCMV in their newborns may cause anxiety and distress to an individual and her family, this will provide the opportunity for appropriate treatment to be provided for her infant and therefore represents an opportunity for early diagnosis and potentially faster treatment for infants. The decision to offer to screen the participants' newborns for cCMV was made following a discussion with our PPI group (the South London Maternal and Paediatric Immunity & Infection Patient and Public Involvement group).

A very small minority of women may be found to have recent infection and as receiving these results may generate anxiety in the women and their families these will be communicated by a clinical member of the team by phone. A letter may subsequently be sent outlining what was said for reference. This group of women will be referred to the Fetal Medicine Unit (FMU) for further investigation and counselling. To expedite this process all such results will be discussed with [name] (or a designated specialist in her absence) to arrange a timely clinic appointment at the FMU. A letter will also be sent to the GP to inform them of the result and the referral to FMU.

11.4 Data handling and analysis

Paper

Paper CRFs will not contain identifiable information. Contact details will be stored in the same folder as the CRF, but will not be attached to it allowing easy separation if necessary. CRFs will be stored in lockable filing cabinets in a secure office. Informed consent forms completed will be collected by a

member of the study team and filed and the file will be stored in a lockable cupboard in a secure office.

Digital

Identifiable information about participants (contact details) will be stored alongside their unique identification number in a password-protected database on a password-protected NHS or University computer. This information is important to allow contact to be made by the study team. Details about investigation results will be stored in a second password-protected database in which participants are only identified by their unique identification number. Information for the study will be entered onto a REDCap database designed by the study team. No identifiable information will be stored in this database. Data will be entered and checked by two separate members of the study team.

12 Archiving arrangements

The trial essential documents along with the trial database will be archived in accordance with the sponsor SOP JRESSOP0016. The agreed archiving period for this trial will be 5 years.

13 Statistical design

13.1 Statistical input in trial design

The statistical aspects of this study have been reviewed by epidemiologist [name].

13.2 Endpoints

The overall aim of the study is to determine the feasibility of future large studies to evaluate the relationship between CMV shedding in pregnancy and congenital CMV. This feasibility study will generate the essential data upon which to appropriately power this study. A key element of determining the sample size for future studies is to estimate the prevalence of CMV shedding in CMV seropositive women during pregnancy.

14.2.1 Primary endpoints

The primary end point (on which this study is powered) is the percentage of subjects with detectable CMV virus (measured via quantitative PCR) in any bodily fluid (saliva, urine or vaginal secretions) at any point in pregnancy

14.2.2 Secondary endpoints

- The percentage of subjects with detectable CMV virus in saliva (measured via quantitative PCR) at individual study visits and cumulatively
- The percentage of subjects with detectable CMV virus in urine (measured via quantitative PCR) at individual study visits and cumulatively

- The percentage of subjects with detectable CMV virus in the vaginal secretions (measured via quantitative PCR) at individual study visits and cumulatively
- The quantity of CMV virus in saliva (measured via quantitative PCR) in the subjects at individual study visits cumulatively
- The quantity of CMV virus in urine (measured via quantitative PCR) in the subjects at individual study visits and cumulatively
- The quantity of CMV virus in vaginal secretions (measured via quantitative PCR) in the subjects at individual study visits and cumulatively
- Risk factors associated with CMV shedding in the subjects
- Assessment of the acceptability of the study procedures to participating pregnant women
- Proportion of subjects approached who are willing to participate in the study
- Proportion of subjects completing the study

14.2.3 Tertiary endpoints

- Detection and quantity of IFN- γ (IU/ml) in the plasma measured by CMV-QuantiFERON ELISA at a study visit when CMV shedding occurs in the subject
- Detection and quantity of IFN- γ (IU/ml) in the plasma measured by CMV-QuantiFERON ELISA at a study visit when CMV shedding does not occur in the subject
- Detection and quantity of IFN- γ (IU/ml) in the plasma measured by ELISPOT-CMV assay at a study visit when CMV shedding occurs in the subject
- Detection and quantity of IFN- γ (IU/ml) in the plasma measured by ELISPOT-CMV assay at a study visit when CMV shedding does not occur in the subject

13.3 Sample size and recruitment

13.3.1 Sample size calculation

This is a feasibility study and the sample size has been calculated to allow an acceptably precise estimate of the percentage of seropositive women who shed CMV during pregnancy.

There is a recently published longitudinal study [Barbosa 2018] looking at the prevalence of CMV shedding throughout pregnancy of CMV seropositive women in Brazil, which found that shedding was detected at least once in 35% of the pregnant women, with saliva being the most common (20%), followed by urine (13.3%), vaginal secretions (12.5%) and blood (0.8%). This study also found that mothers living with or providing daily care to young children were twice as likely to shed CMV at least once compared to women with less exposure to young children (58% vs 26%).

Based on this study, the sample size was calculated using an estimated proportion (prevalence of CMV shedding at least once in any bodily fluid in CMV seropositive women throughout pregnancy) of 30%. Thus a sample size of 200 participants, which is feasible in practice, will provide tight 95% confidence levels for this estimate of +/-6% (i.e. 24-36%).

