Up to 15% of infants infected with cCMV have symptoms at birth. Of those infants who are initially asymptomatic, up to 15% will be symptomatic later in life. About one-fifth of children with cCMV will have life-long problems, of which sensorineural hearing loss (SNHL) is the most common. Other problems include visual impairment, learning difficulties, movement problems and epilepsy. The most severely affected children need life-long support with everyday activities, placing emotional and financial strain on their families and requiring significant input from health and social care services [Dollard 2007].

Despite the burden of adverse health outcomes, most pregnant women are not aware of CMV infection or the simple measures that can be taken to prevent it. Advice about avoidance of CMV infection is not routinely offered in the NHS. There is no licensed CMV vaccine and no routine treatment of antenatal CMV in the NHS. This may be a reflection of the limited knowledge on CMV infection in pregnancy and its relationship with cCMV.

The natural history of CMV in pregnancy is complex, because maternal primary infection, maternal reinfection with a new strain or reactivation of latent infection can all result in intrauterine transmission of CMV [de Vries 2013; Mussi-Pinhata 2018].

CMV shedding

Shedding of CMV in those with latent infection may be common and has been demonstrated in different samples (blood, saliva, urine, cervical secretions, breast milk) in pregnant women during primary infection, reactivation of endogenous latent virus, or following reinfection with a new strain of CMV [Barbosa 2018; Atkinson 2014; Kimberlin 2003; Cannon 2011]. However, the pattern and intensity of CMV shedding and its association with vertical transmission and cCMV is not well defined [Williams 2015; Marty 2017; Pass 2009; Sabbaj 2011; Griffiths 2011].

In a longitudinal study looking at the prevalence of CMV shedding throughout pregnancy of seropositive women in a high seroprevalence setting [Barbosa 2018], shedding was detected at least once in 35% of the pregnant women, with saliva being the most common (20%), followed by urine (13.3%), vaginal secretions (12.5%) and blood (0.8%). This study also found that mothers living with or providing daily care to young children were twice as likely to shed CMV at least once compared to women with less exposure to young children (58% vs 26%).

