6.1 Inclusion criteria

- Pregnant
- CMV seropositive
- Willing and able to provide informed consent
- Living with child(ren), at least one of whom is less than four years old
- Willing to have saliva, urine and vaginal secretion sampling
- Willing to be followed up until postpartum period

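### Does it matter that the sample size assumes 30% shedding when the study it cites reports 35% overall and 58% in mothers of young children?

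*Combined protocol and SAP*

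**What the plan says.** Section 13.3.1 sizes the study for the precision of a single proportion: the percentage of women with CMV detected in saliva, urine or vaginal secretions at any time in pregnancy. Section 14.2.1 calls this "The primary end point (on which this study is powered").

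Section 13.3.1 summarises one published cohort. There, "shedding was detected at least once in 35% of the pregnant women", and women living with or caring daily for young children shed more often "compared to women with less exposure to young children (58% vs 26" percent). The next paragraph begins "Based on this study, the sample size was calculated using an estimated proportion" and gives that proportion as 30%. It concludes that 200 women "will provide tight 95% confidence levels for this estimate of +/-6% (i.e. 24-36" percent).

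Three other places bear on the point:

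- Section 6.1 requires every participant to be "Living with child(ren), at least one of whom is less than four years old".
- The background text on CMV shedding says the cited cohort was followed "throughout pregnancy of seropositive women in a high seroprevalence setting", whereas section 13.3.2 assumes that 55% of the local population is seropositive.
- Section 13.2 says "A key element of determining the sample size for future studies is to estimate the prevalence of CMV shedding", so the estimate is meant to feed later designs.

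**The concern.** The 30% is none of the three any-shedding figures in the source to which it is attributed. Among those three, 58% describes the group closest to the women eligible here. If the planning value is about half the relevant rate, the printed 24 to 36% interval could be in the wrong place as well as too narrow: an interval centred on 58% would not overlap it. The stated precision would also read 7 points instead of 6 at both cited figures, 35% and 58%.

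This is the only planning figure for the primary endpoint, and later studies will be sized on the prevalence found. If the assumption were both unsupported and influential, the study might deliver less precision than promised on its main result.

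**Working it through.** **Inputs.** From section 13.3.1: n = 200, 95% confidence, planning proportion 30%, cited proportions 35%, 58% and 26%, and blood positivity of 0.8%. Section 13.4.2 asks for a 95% confidence interval without naming a method.

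**Step 1: reproduce the stated figure.** The Wald half-width is 1.96 × √[p(1 − p)/n].

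At p = 0.30: 1.96 × √(0.30 × 0.70/200) = 1.96 × 0.0324 = 6.35 points, or 23.65 to 36.35%. This rounds to the plan's 6 points and 24 to 36%, so the arithmetic is right.

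**Step 2: vary the prevalence with n = 200.**

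| Prevalence | Wald half-width | Wald interval | Exact (Clopper-Pearson) half-width |
|---|---|---|---|
| 30% | 6.35 | 23.65–36.35% | 6.56 |
| 35% | 6.61 | 28.39–41.61% | 6.82 |
| 58% | 6.84 | 51.16–64.84% | 7.05 |
| 50% (worst case) | 6.93 | 43.07–56.93% | 7.13 |

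On the Wald scale the loss from 30% is 6.61 − 6.35 = 0.26 points at 35%, 6.84 − 6.35 = 0.49 at 58%, and 6.93 − 6.35 = 0.58 at worst. The step from 6 to 7 appears because these values fall either side of 6.5. It also depends on the method: the exact half-width at 30% is 6.56, which already rounds to 7.

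**Step 3: what it would cost to hold 6.35 points.** This takes 217 women at 35% and 233 at 58%, that is 17 or 33 more women to recover 0.26 or 0.49 points.

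**Step 4: can 30% be derived from the cited figures?** Leaving out blood, which this endpoint does not use, lowers 35% to 35 − 0.8 = 34.2% at the least. As a mixture of the two exposure groups, 30% would need (30 − 26)/(58 − 26) = 12.5% exposed women, and here all are exposed. Neither route gives 30%, so the value is a judgement that the plan leaves unexplained.

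**Step 5: where does the 30% enter later?** Section 13.4.2 computes the observed percentage and its interval from the study's own data. The 30% appears in no model, threshold or decision rule. The prevalence that section 13.2 passes to future designs is the observed one.

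**The case for a change.** The strongest case for a change is about location more than width. The source reports 58% for women much like these, yet the plan prints 24 to 36% as its expected interval. A result near 58% would look surprising beside that range, although the plan's own reference had reported it. One sentence would fix this at almost no cost.

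Part of this stands. The 30% is unexplained, and 58% is the nearest cited match. The rest is weaker:

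- The documents do not show that 30% is wrong. The cited cohort comes from a high-seroprevalence setting. Its 58% group also includes women giving daily care to children. The protocol does not report how that study defined young children, how often it sampled or how large the group was. A lower value for this cohort is defensible, and planning on 58% would be just as debatable.
- Nothing is hidden. Section 13.3.1 prints the 35%, 58% and 26% immediately before the 30%, so a reader can see the gap and judge it.
- A planning interval is not a prediction against which the result is tested. Its job is to show that n is adequate, and n = 200 is adequate across the whole range.

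**Conclusion.** No change follows. The stated precision is correct for the stated prevalence, and the design is robust to that assumption: with 200 women analysed, the half-width stays at or below 6.93 points (Wald) or 7.13 points (exact) at any prevalence. Moving from 30% to the cited 35% or 58% costs 0.26 or 0.49 points. Section 13.3.1 asks only for an acceptably precise estimate in a feasibility study and justifies 200 partly by practicality, so no numerical target is missed. Enrolment, sampling, the primary analysis and its interpretation all stay as they are.

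The missing reason for 30% is a small gap in reporting that has no effect on the results. The conclusion assumes that about 200 women contribute to the primary analysis. With 180, the Wald half-widths would be 6.69, 6.97 and 7.21 points at 30%, 35% and 58%. At 30%, losing 20 women costs 6.69 − 6.35 = 0.34 points, more than moving the assumed prevalence from 30% to 35%. Whether 58% applies to this London cohort cannot be settled from the documents, and the study's own data will answer it.

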13.3.2 Planned recruitment rate

For the parallel-run RACEFIT study, approximately 4800 women is estimated to be approached over a one-year recruitment period (approximately 400 per month). The RACE-Fit study team have estimated from their experience that 70% of women approached will consent to serological screening of a blood sample taken with their routine antenatal bloods and 50% of those to consent to taking part in the full study. Approximately 23% of women approached are eligible for the screening process. Assuming that 55% [Tookey 1992] of the population will be CMV seropositive, it means that 212 ($4800 \times 23\% \times 70\% \times 50\% \times 55\%$) women from those approached are expected to take part in the study over 12 months. Therefore, a sample size of 200 participants over 12-month recruitment period should be achievable.

13.4 Statistical analysis plan

13.4.1 Summary of baseline data and flow of patients

Baseline data will be summarised descriptively. The percentage of eligible women consenting to participate will be calculated as (number consenting) / (number of eligible women identified to be CMV seropositive from the screening). To assess the representativeness of women participating in the study, characteristics of those consenting (ethnicity and age) will be compared to those who do not consent in univariate analyses (e.g. using chi squared and t tests).

13.4.2 Primary endpoint analysis

The percentage of participating women with at least one study sample with CMV DNA detected (saliva, urine or vaginal secretions taken at any study visit during pregnancy) as measured by PCR, will be calculated with 95% confidence intervals (CIs).

13.4.3 Secondary endpoint analysis

For each sample type (saliva, urine, vaginal secretions), the percentage of participating women with detectable CMV DNA as measured by quantitative PCR, will be calculated for each study visit (Visit 1, Visit 2, Visit 3, Visit 4), and cumulatively, with 95% CIs.

For each study visit (Visit 1, Visit 2, Visit 3, Visit 4), the percentage of participating women with detectable CMV DNA as measured by PCR, will be calculated for each sample type (saliva, urine, vaginal secretions), and cumulatively, with 95% CIs

CMV shedding will also be assessed quantitatively, as measured by quantitative PCR on the amount of CMV DNA detected, in each sample type and at each study visit, separately and cumulatively, with 95% CIs.

The distributions of sample type, study visit number, detectable shedding and quantity of shedding will be summarised graphically and described using means and medians, as appropriate.

Factors associated with CMV shedding as a binary outcome (detectable shedding versus no detectable shedding) will be investigated using multivariable mixed effects models. Potential risk factors will be those assessed using the study sociodemographic questionnaire at Visit 1 and risk factor questionnaires at all visits (these variables may be time-varying) – these will include ethnicity, age, number of children, parental occupation, age of child(ren), and type of handling with child(ren)'s urine and saliva.

Acceptability of the study design and procedures will be analysed descriptively, for example by calculating mean scores derived from satisfaction scales. We will also investigate factors associated with satisfaction, defined as a binary variable, using logistic regression. We will summarise free text comments made through the feedback questionnaire.

The percentage of eligible women who consent to participate, and the percentage of participants who complete the study (provide urine, saliva and vaginal secretion samples and questionnaire data at all four study visits, with or without blood and newborn saliva samples), will be calculated.

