Criteria for evaluation	
Primary outcome measure(s)
 
 • The prevalence of CMV shedding in saliva, urine and vaginal secretions of CMV seropositive women throughout pregnancy 
Secondary outcome measure(s)
 
 • The quantity of CMV shedding in saliva, urine and vaginal secretions of CMV seropositive women throughout pregnancy • The fold-differences in the prevalence and quantity of CMV shedding in saliva, urine and vaginal secretions in CMV seropositive women throughout pregnancy • The fold-differences in the prevalence and quantity of CMV

	
shedding in saliva, urine and vaginal secretions between different gestational stages of pregnancy in CMV seropositive women
 
 • The risk factors for CMV shedding in CMV seropositive pregnant women • The acceptability of the study procedures to participating pregnant women • The proportion of women approached who are recruited into the study • The proportion of participants completing the study • The relationship between cellular mediated CMV-specific immunity and CMV shedding in CMV seropositive pregnant women
	
Tertiary outcome measure(s)
 
 • The fold-differences in CMV-specific T cell immune responses, as measured by QuantiFERON-CMV and CMV-ELISPOT assays, in the evaluation of CMV-specific T cell responses with CMV shedding in CMV seropositive pregnant women
Sources of funding	Merck Investigator Studies Program
Anticipated start date:	March 2018
Anticipated primary completion date:	April 2021
Sponsor/Co-Sponsor	St George's, University of London
Key Contact names	
Sponsor contact: [name] Email: [contact] [contact]
 
Chief Investigator: [name] Email: [contact] [contact]
 
Principal Investigator: [name] Email: [contact] [contact]

Congenital cytomegalovirus (cCMV)

cCMV is the most common congenital infection in the UK. With an estimated incidence of 3 per 1000 live births (approximately 2400 cases in the UK annually) [Peckham 1983; Griffiths 1991], it is more common than many better known congenital conditions, such as Down's syndrome, spina bifida and cystic fibrosis [Dollard 2007].

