4.1 Primary objective

- To evaluate the prevalence of CMV shedding in saliva, urine and vaginal secretions of CMV seropositive women throughout pregnancy.

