4.2 Secondary objectives

- To evaluate the quantity of CMV shedding in saliva, urine and vaginal secretions of CMV seropositive women throughout pregnancy
- To compare the prevalence and quantity of CMV shedding in saliva, urine and vaginal secretions in CMV seropositive women throughout pregnancy

- To compare the prevalence and quantity of CMV shedding between different gestational stages of pregnancy in CMV seropositive women
- To identify risk factors for CMV shedding in CMV seropositive pregnant women
- To evaluate the acceptability of the study procedures to the participating pregnant women
- To evaluate the proportion of women approached who are recruited into the study
- To evaluate the proportion of participants completing the study
- To evaluate the relationship between cellular mediated CMV-specific immunity and CMV shedding in CMV seropositive pregnant women

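### The cumulative shedding figures for each fluid, read plainly, take in the postpartum Visit 4 although the objectives concern pregnancy; separately, the four-visit completion rule conflicts with the preterm-delivery rule

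*Combined protocol and SAP*

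**What the plan says.** All references are to the combined protocol and SAP.

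- **Primary.** Section 14.2.1 counts detection "in any bodily fluid (saliva, urine or vaginal secretions) at any point in pregnancy". Section 13.4.2 repeats the limit: "saliva, urine or vaginal secretions taken at any study visit during pregnancy".
- **Fluid-specific percentages.** Section 14.2.2 has no such limit; for saliva it reads "The percentage of subjects with detectable CMV virus in saliva (measured via quantitative PCR) at individual study visits and cumulatively", with matching items for urine and vaginal secretions. Section 13.4.3 says the percentage for each fluid "will be calculated for each study visit (Visit 1, Visit 2, Visit 3, Visit 4), and cumulatively, with 95% CIs".
- **Quantity.** Section 13.4.3 assesses it "in each sample type and at each study visit, separately and cumulatively, with 95% CIs", again with no pregnancy limit.
- **Objectives.** Section 4.1 reads "To evaluate the prevalence of CMV shedding in saliva, urine and vaginal secretions of CMV seropositive women throughout pregnancy". The synopsis (section 2) gives as a secondary outcome "The quantity of CMV shedding in saliva, urine and vaginal secretions of CMV seropositive women throughout pregnancy", and section 4.2 matches it.
- **Visit 4.** Section 9.3 places it between birth and one week afterwards. Section 9.3.4 collects the same three maternal samples there.
- **Preterm delivery.** Under section 9.3.4 the visit after a premature birth takes the next visit number, and nothing more is required. In its example, a woman last seen at Visit 2 has a postpartum visit labelled Visit 3, which the text equates with Visit 4.
- **Completion.** Section 13.4.3 requires the three maternal samples and questionnaire data at all four visits, and makes no exception.

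**The concern.** The objectives concern shedding in pregnancy, and the primary is restricted to match. The fluid-specific cumulative figures are not. If they run over the four visits listed, they cover a wider window than the primary. A reader would expect the saliva, urine and vaginal percentages to be parts of the any-fluid percentage, but a woman who first sheds after birth would enter a fluid's total and not the primary. Cumulative quantity would likewise mix pregnancy and postpartum values.

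The second matter is independent of the first. Completion is a named feasibility outcome in a study whose aim is feasibility. A woman who delivers preterm before Visit 3, and does everything then asked of her, is recorded as a non-completer. The rate would therefore combine dropout with schedules that the protocol itself cut short.

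**Working it through.** **Plan's own figure.** Section 13.3.1 gives 30% ± 6% with 200 women. 1.96 × √(0.30 × 0.70 / 200) = 6.35 points, which rounds to the stated 6. It concerns the primary and is not in dispute.

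**The window, by reading.** Take a woman negative in all fluids at Visits 1 to 3 and saliva-positive at Visit 4. Under section 13.4.2 she is negative, because the only positive sample was not taken during pregnancy. Under section 13.4.3, accumulating over the four listed visits, she is positive for saliva. The two rules classify her differently.

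**Possible size.** Inputs from section 13.3.1: N = 200, and the cited study's rates of 20% (saliva), 13.3% (urine) and 12.5% (vaginal secretions). Assumptions that the documents do not supply:

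- these rates are cumulative over three pregnancy visits;
- the postpartum rate equals the per-visit pregnancy rate;
- all 200 women give Visit 4 samples;
- within-woman correlation ρ lies anywhere from 0 to 1.

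For independent visits (ρ = 0), the per-visit rate is p = 1 − (1 − P)^(1/3) and the four-visit figure is 1 − (1 − P)(1 − p):

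- Saliva: p = 7.17%; 1 − 0.800 × 0.9283 = 25.7%
- Urine: p = 4.65%; 1 − 0.867 × 0.9535 = 17.3%
- Vaginal secretions: p = 4.35%; 1 − 0.875 × 0.9565 = 16.3%

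For 0 < ρ < 1, use a beta-binomial: with s = (1 − ρ)/ρ and b = (1 − p)s, the chance of no positive in k visits is the product of (b + i)/(s + i) for i = 0 to k − 1. Solve p so that three visits give P, then take k = 4. For saliva at ρ = 0.4, s = 1.5 and p = 10.55%, so b = 1.342. Three visits give 0.800, and the fourth factor is 4.342/4.5 = 0.965. The four-visit figure is 1 − 0.772 = 22.8%.

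The 95% half-width is 1.96 × √(P(1 − P)/200).

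| Fluid | Three visits | Four visits, ρ = 0 | Shift, ρ = 0 | Shift, ρ = 0.4 | Shift, ρ = 1 | Half-width |
|---|---|---|---|---|---|---|
| Saliva | 20.0% | 25.7% | 5.7 | 2.8 | 0 | 5.5 |
| Urine | 13.3% | 17.3% | 4.0 | 2.0 | 0 | 4.7 |
| Vaginal | 12.5% | 16.3% | 3.8 | 1.9 | 0 | 4.6 |

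Shifts and half-widths are in percentage points. The ρ = 0 shifts correspond to about 11.5, 8.1 and 7.6 extra positive women out of 200.

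**Completion.** In the example in section 9.3.4 three visits are possible, while section 13.4.3 requires four. Each such woman lowers the rate by 1/200 = 0.5 point. The documents do not say how many to expect.

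**The case against.** **The window is not wholly undefined.** One might infer that the plan gives no window at all. That goes too far: read plainly, section 13.4.3 gives a Visit 1 to 4 total, which is a permissible descriptive summary. The exact fault is that it does not match the objectives or the primary. The mismatch is not quite clean either. Section 9.3 uses the throughout-pregnancy phrase loosely when justifying the four-visit schedule, and a running total by visit would yield a pregnancy figure at Visit 3. The text does not say that a running total is meant.

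**Postpartum shedding stays visible.** Visit 4 has its own row for each fluid. That stands, but visit rows alone do not recover a pregnancy-only cumulative percentage, because they do not show which women overlap.

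**The magnitude is all assumption.** This stands. At ρ = 0.4 the shifts lie inside the half-widths. Nor is the range a true bound. Section 13.3.1 reports 58% against 26% shedding by exposure to young children, and this study enrols women living with a child under four, so the base rates may differ. A postpartum rate above the pregnancy rate would enlarge the shifts, but nothing in the documents supports assuming one. The half-widths give scale only, since a change in what is estimated is not sampling error.

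**The strict completion count is legitimate.** It is explicit and reproducible, and a preterm birth after Visit 3 is not caught. This stands as a reason to keep the count, but not as a reason to leave sections 9.3.4 and 13.4.3 unreconciled.

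**Further inferences are weak.** A reader might suppose that relabelled preterm visits will contaminate the Visit 3 results; section 9.3.4 largely answers this by equating them with Visit 4. One might also suppose that the risk-factor model departs from its objective, "To identify risk factors for CMV shedding in CMV seropositive pregnant women", by including Visit 4. The sentence about all visits describes when questionnaires are taken and does not settle which outcomes are modelled. The unnamed three time points in section 13.4.5 are unclear, but they do not show that the wrong visits will be used.

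**Conclusion.** The point holds, and it is minor. Followed as written, section 13.4.3 counts postpartum-only shedders in each fluid's cumulative figure, against the pregnancy wording of the objectives and the primary. It also records as a non-completer a woman whom section 9.3.4 excuses from further visits.

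Only secondary and feasibility outcomes are touched. A reader might infer that the prevalence meant for sizing later studies (section 13.2) is at risk. It is not: the primary carries its own pregnancy limit. The sample size and the across-fluid totals within a single visit are unaffected as well.

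The percentage shifts run from nothing, when a woman's results agree perfectly across visits, up to the independent-visit values in the table. They are illustrations resting on an equal postpartum rate and a three-visit reading of the cited rates, and the documents confirm neither. The classification mismatch does not depend on those assumptions.

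**What to change.** 1. In sections 14.2.2 and 13.4.3, base each fluid's cumulative percentage and quantity on samples from visits made before delivery. Classify each visit as before or after delivery, not by visit number, which fails for a relabelled preterm visit, nor by date alone. Visit 4 can begin at birth, and the labelling section (10.6.2) records time of sampling only for blood, so a swab or urine sample from the day of birth could not be placed by date.
2. Report the postpartum visit in its own row, including a preterm visit labelled Visit 3 but treated as Visit 4. Give any Visit 1 to 4 total a separate name.
3. Reconcile sections 9.3.4 and 13.4.3 by reporting completion against the visits required of each woman, beside the strict four-visit figure already planned.

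The cost is analysis wording. It needs no extra samples or visits. The documents do not say that delivery date is entered on the CRF, so a before/after-delivery flag per visit should be confirmed or added; the team must already know when birth occurred in order to time Visit 4.
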